3.3. Benefit/Risk Assessment

More information about the known and expected benefits, risks, and reasonably anticipated AEs of galcanezumab may be found in the IB. Information on AEs expected to be related to the investigational product may be found in Section 7 (Development Core Safety Information) of the IB. Information on SAEs expected in the study population independent of drug exposure and that will be assessed by the sponsor in aggregate periodically during the course of the study, may be found in Section 6 (Effects in Humans) of the IB.

4. Objectives and Endpoints

Table 4.1 shows the objectives and endpoints of the study.

Table 4.1. Objectives and Endpoints

Objectives	Endpoints

Primary To evaluate the safety of open-label galcanezumab within the context of expected medical practice in eligible patients with episodic or chronic cluster headache.
	
Analysis of:
 
 • TEAEs • SAEs • Suicidal ideation and behaviors assessed by solicited questioning using the C-SSRS

Secondary To characterize the reasons for discontinuation and AEs of interest for galcanezumab. To characterize the immunogenicity of galcanezumab.
	
Discontinuation rates
 
Analysis of:
 
 • Injection-site reactions • Allergy/hypersensitivity • Infections • The development and consequences of ADAs to galcanezumab, their relationship with AEs, and neutralizing ADAs to galcanezumab

Tertiary To evaluate the effectiveness of galcanezumab. To evaluate the effect of galcanezumab on health values.
	
 • The proportion of patients reporting a score of 1 (“very much better”) or 2 (“much better”) on the PGI-I 1 month after receiving their first dose will be reported. 
EQ-5D-5L Analysis of:
 
 • Health state index values • Each dimension of the descriptive system and dichotomized level responses • EQ-VAS current health score • Correlations with PGI-I, cluster headache status

Abbreviations: ADA = anti-drug antibodies; C-SSRS = Columbia-Suicide Severity Rating Scale; EQ-5D-5L Analysis = European quality 5-dimensions 5-levels; EQ-VAS = European Quality Visual Analogue Scale; PGI-I = Patient Global Impression of Improvement; SAE = serious adverse event; TEAE = treatment-emergent adverse event.

5. Study Design

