5.1. Overall Design

Study CGAR is a Phase 3b single-arm, open-label safety study of galcanezumab 300 mg in outpatients with episodic or chronic cluster headache who completed Study CGAL or Study CGAM.

Please refer to the Protocol Operations Manual for information regarding the schedule of activities, study design, study tools, and patient scenario examples.

The study will consist of 2 SP:

- SP I is the screening phase to confirm patients meet the inclusion/exclusion criteria.
- SP II is the open-label treatment phase during which patients can receive galcanezumab 300 mg administered subcutaneously (SC) up to once a month.

Study Phase I: SP I is the screening phase. Patients will sign an informed consent document prior to completing any study-related screening procedures. SP I is the time from Visit (V)1 to V2. The minimum timeframe for SP1 needs to allow sufficient time for patients to washout of any excluded medications and to review subject eligibility. Visit 1 will be considered complete when the last procedure of the screening assessment for the patient is completed. Once Study CGAR is open for enrollment, potentially eligible patients may enter screening directly from the parent study, CGAL or CGAM. If a patient is not experiencing cluster headache attacks (e.g., in remission) they may wait to enter screening for CGAR until they anticipate experiencing or are experiencing a cluster headache attack. If patients had completed the parent study, CGAL or CGAM, prior to Study CGAR being open for enrollment, potentially eligible patients may still enter screening for Study CGAR. Study procedures for V1 (Event List A) of Study CGAR will be completed as follows:

- If the last visit of the parent study is also the first visit of Study CGAR, then electrocardiograms (ECGs), vitals, weight, hematology, clinical chemistry, urinalysis, hemoglobin A1C (HbA_{1C}), and serum pregnancy, C-SSRS, and Self-Harm Supplement Form/ Self-Harm Follow-up Form (SHSF/SHFU) from the last visit of the parent study will also be used for the first visit of Study CGAR.
- If the last visit of the parent study is ≤ 2 weeks from V1 of Study CGAR, the hematology, chemistry, HbA_{1C}, and urinalysis do not need to be repeated.
- If the last visit of the parent study is > 2 weeks from V1 of Study CGAR, all study procedures in Event List A need to be completed at the first visit of Study CGAR.

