9.9. Health Economics

The self-reported questionnaires will be administered according to the Schedule of Activities ([Table 2.1](#)) in countries where the questionnaires have been translated into the native language of the region and linguistically validated.

European Quality of Life Questionnaire 5-Dimensions 5-Levels (EQ-5D-5L) (EuroQoL Group): A generic, multidimensional, health-related, quality-of-life instrument that contains 2 parts: a health status profile and a VAS to rate global health-related quality of life. The profile allows patients to rate their health state on that day within 5 domains, including: mobility, self-care, usual activities, pain/discomfort, and anxiety/depression (Brooks 1996; Herdman et al. 2011; Stafford et al. 2012). A single score between 1 and 5 is generated for each domain with all 5 domains being mapped to a single index through an algorithm (Van Reenen and Janssen 2015). The index ranges between 0 and 1 with the higher score indicating a better health state perceived by the patient. The VAS provides an overall patient rating of health status on that day, with a range from 0 (i.e., “worst imaginable health state”) to 100 (i.e., “best imaginable health state”) serving as anchors for the patient’s numeric rating on the hash-marked, vertical VAS.

The EQ-5D-5L and cluster headache status data (Section 9.10) will be used to characterize changes in the health status of patient groups. The PGI-I, and other patient characteristics or clinical information may also be used to define specific patient groups associated with EQ-5D-5L outcomes.

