9.10. Cluster Headache Attack Assessments

The cluster headache status questions will collect information on the following: if a patient is currently in a bout, the duration of the current bout or time since the last bout; and questions related to attacks that occurred over a 24-hour period (i.e., yesterday from midnight to midnight). Patients will be asked to record the number of cluster headache attacks during that time period, information regarding abortive medication use, cluster headache attack duration, and cluster headache attack pain severity will also be recorded. Pain severity will be rated using a 5-point pain scale, where 0=no pain, 1=mild pain, 2=moderate pain, 3=severe pain, and 4=very severe pain. Patients should record all cluster attacks regardless of attack duration.

10. Statistical Considerations

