5.5. Adjustments for Covariates

Statistical modeling of data using covariates is not anticipated in this study. However, such modeling may be performed as post hoc analyses if deemed appropriate.

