Descriptive statistics (n, mean, standard deviation [SD], range, median, 25th and 75th percentiles, min, max) for EQ-5D-5L Health State Index overall score based on US and UK population, scores for each of the 5 EQ-5D-5L dimensions (mobility, self-care, usual activities, pain/discomfort, and anxiety/depression), and EQ-5D-5L VAS current health score will be provided by visit. The number and percentage of patients with dichotomized responses (problems, no problems) for each of the 5 EQ-5D-5L dimensions will also be provided by visit.

To assess the correlation of EQ-5D-5L Health State Index Scores and VAS current health score with PGI-I and cluster headache status, the following analyses will also be performed:

- A correlation analysis between mean change from baseline in EQ-5D-5L with PGI-I at month 1, using Spearman's rank correlation coefficient.
- An Analysis of Variance (ANOVA) comparing mean change from baseline in EQ-5D-5L by cluster headache status (active or remission) at month 1 and month 6.

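### The EQ-5D-5L ANOVA by cluster headache status ignores status at first dose, so it cannot isolate the change that goes with moving from active to remission

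*SAP*

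**What the plan says.** Protocol Table 4.1 lists, among the tertiary EQ-5D-5L endpoints, "Correlations with PGI-I, cluster headache status". SAP 5.14 gives the purpose as "To assess the correlation of EQ-5D-5L Health State Index Scores and VAS current health score with PGI-I and cluster headache status" and specifies two analyses. One is a Spearman correlation with PGI-I at month 1. The other is an ANOVA "comparing mean change from baseline in EQ-5D-5L by cluster headache status (active or remission) at month 1 and month 6". The ANOVA is the only analysis specified for the status part of the endpoint.

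SAP 5.14 names no baseline status, no transition groups and no restriction on who is compared. SAP 5.5 adds: "Statistical modeling of data using covariates is not anticipated in this study". SAP 5.4 places baseline in SP I before the first dose, whatever the patient's bout status.

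On entry, Protocol 5.1 says of patients who are not having attacks that "they may wait to enter screening for CGAR until they anticipate experiencing or are experiencing a cluster headache attack". Its note on a late V2 gives a patient who is in remission at V1 as the example. Nothing in Protocol 6.1 or 6.2 requires a bout at the first dose.

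On data, Protocol 9.10 says the status questions record "if a patient is currently in a bout, the duration of the current bout or time since the last bout". Table 2.1 schedules both these questions and the EQ-5D-5L at V1, Month 0, Month 1 and Month 6. Protocol 9.9 states the intended use: "The EQ-5D-5L and cluster headache status data (Section 9.10) will be used to characterize changes in the health status of patient groups".

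**The concern.** A change score has two ends, but the grouping describes only one of them. The Month 1 remission group can hold patients who were in a bout at first dose and came out of it, whose EQ-5D-5L would be expected to rise. It can also hold patients who were out of a bout both times, for whom little change would be expected. The Month 1 active group can likewise hold patients in a bout throughout and patients dosed before a bout that then began.

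The difference between the two group means therefore reflects two things at once: how EQ-5D-5L differs in and out of a bout, and the case mix at first dose. The planned tables do not let a reader separate them. The baseline characteristics in SAP 5.10 include the number of attacks yesterday but not bout status, and no table crosses baseline with follow-up status.

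At stake is whether the one analysis of EQ-5D-5L against status can be interpreted.

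**Working it through.** The plan gives no figure for this analysis, so there is nothing to reproduce. The check is algebra with assumed inputs, followed by a simulation.

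**Inputs, none of them given in the documents**
- D: EQ-5D-5L difference between out of a bout and in a bout. Results are in units of D, with D = 0.20 on the index as an illustration.
- a: share of patients out of a bout at first dose, 0 to 0.5.
- s: probability of being out of a bout at Month 1 for those in a bout at first dose, 0.2 to 0.5.
- k: the same probability for those out of a bout at first dose, 0.3 to 0.9.
- Simplification: EQ-5D-5L moves only when bout status moves.

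**Formulas**
- Share in remission at Month 1: R = a·k + (1 − a)·s.
- Share of the remission group already out of a bout at first dose: q = a·k / R.
- Share of the active group out of a bout at first dose: r = a·(1 − k) / (1 − R).
- Mean change: (1 − q)·D in the remission group and −r·D in the active group.
- ANOVA contrast: (1 − q + r)·D.

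**Worked case**, a = 0.3, s = 0.3, k = 0.9:
- R = 0.27 + 0.21 = 0.48
- q = 0.27 / 0.48 = 0.563
- r = 0.03 / 0.52 = 0.058
- contrast = (1 − 0.563 + 0.058)·D = 0.495 D, or 0.099 when D = 0.20

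| a | s | k | q | r | Remission mean (D) | Contrast (D) | Contrast, D = 0.20 |
|---|---|---|---|---|---|---|---|
| 0 | 0.3 | 0.9 | 0 | 0 | 1.000 | 1.000 | 0.200 |
| 0.1 | 0.3 | 0.9 | 0.250 | 0.016 | 0.750 | 0.766 | 0.153 |
| 0.2 | 0.3 | 0.9 | 0.429 | 0.034 | 0.571 | 0.606 | 0.121 |
| 0.3 | 0.3 | 0.9 | 0.563 | 0.058 | 0.438 | 0.495 | 0.099 |
| 0.5 | 0.3 | 0.9 | 0.750 | 0.125 | 0.250 | 0.375 | 0.075 |
| 0.3 | 0.3 | 0.3 | 0.300 | 0.300 | 0.700 | 1.000 | 0.200 |
| 0.3 | 0.5 | 0.3 | 0.205 | 0.375 | 0.795 | 1.170 | 0.234 |

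Over the whole grid the contrast runs from 0.29 D (a = 0.5, s = 0.2, k = 0.9) to 1.21 D (a = 0.5, s = 0.5, k = 0.3). Three patterns follow:
- With a = 0 there is no bias.
- With k = s the contrast is D, although the remission-group mean is still diluted to (1 − a)·D.
- With k > s the contrast is too small; with k < s it is too large.

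**Simulation** of the worked case (200,000 patients, D = 0.20, assumed between-patient SD 0.15 and measurement SD 0.10):

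| Analysis | Estimate |
|---|---|
| As in SAP 5.14 | 0.098 |
| Only patients in a bout at first dose | 0.199 |
| Status at first dose added as a factor | 0.199 |
| Baseline EQ-5D-5L score as covariate, no baseline status | 0.140 |

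Restricting on baseline status, or adding it as a factor, recovers D. Adjusting for the baseline score alone does not in this scenario.

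**The case against.** The strongest reply is that the SAP promises a correlation, not the effect of remission. An unadjusted ANOVA can report that a larger change goes with one status than with the other. A reader might infer that the plan claims to measure what remission does to health values and fails. The documents do not support that: no section sets the effect of remission as an objective. What stands against the reply is Protocol 9.9, which wants the data to describe changes in health status of patient groups. A patient who has just remitted and one who was never in a bout are different groups for that question.

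Second, the passage on anticipated attacks governs entry to screening, not dosing. The late-V2 note suggests that dosing may wait for a patient in remission at V1, and Protocol 3.1 ties dosing to symptoms and response. So a first dose outside a bout is allowed, but it would be wrong to infer that it is common. This stands, and it is why the share is treated as unknown.

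Third, the months named in the sentence could modify the change rather than the status. If so, the SAP does not say when status is taken, and the text still needs a clarification.

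Fourth, the protocol leaves room for a better analysis. Section 10.3.6.1 says clinical variables will be considered for EQ-5D-5L changes, Section 9.9 allows other clinical information to define groups, and the SAP permits post hoc modelling. None of these specifies a split by baseline status.

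**Conclusion.** The point holds as a limit on interpretation. Under the likelier reading of SAP 5.14, the contrast mixes status transitions and cannot isolate the change that goes with moving from active to remission. The bias can go either way. It is zero if every patient is in a bout at first dose, or if status at first dose does not predict later status; the documents establish neither. A reader might conclude that the analysis shows nothing about remission, or that it always understates the difference. Neither follows.

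The range of 0.29 D to 1.21 D rests wholly on assumed shares and on the simplification that EQ-5D-5L moves only with bout status. It shows sensitivity and is not an estimate of the error in this trial.

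The weight is low. This is one analysis under a tertiary endpoint of a single-arm safety study, and no primary or secondary conclusion depends on it. It is still worth changing, because the correction is cheap and the data are already scheduled.

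**What to change.** In SAP 5.14:
1. State that active or remission is taken from the question on whether the patient is currently in a bout, at Month 0 (last pre-dose record) and at Month 1 or Month 6.
2. Report n and mean EQ-5D-5L change for the four baseline-by-follow-up cells: active/active, active/remission, remission/active and remission/remission.
3. Base the active versus remission comparison on patients in a bout at Month 0, or keep all patients and include Month 0 bout status as a factor in the ANOVA. The second choice needs a stated exception to SAP 5.5.
4. Baseline EQ-5D-5L may be added as a covariate, but it does not replace baseline status.
5. Describe the result as an association. Even after the change, the groups are defined by a post-dose outcome, so the comparison does not give a causal effect of remission.

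The cost is SAP wording and one extra table, with no new data collection. Some cells may be small. Restriction drops patients who were out of a bout at Month 0, in a study whose size was not set for this comparison; the factor version keeps them.

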5.15. Bioanalytical and Pharmacokinetic/Pharmacodynamic Methods

Bioanalytical and Pharmacokinetic/Pharmacodynamic (PK/PD) methods are not applicable to this SAP. An analysis of PK/PD data is not planned as part of this SAP but will be documented separately according to global PK/PD procedures.

5.16. Safety Analyses

For purposes of the cluster headache regulatory submission, analyses of Study CGAR safety data are more thoroughly assessed in the context of combining the safety data from the parent studies with the safety data from Study CGAR. The planned integrated analyses are described in separate documents. For the purpose of Study CGAR alone, the safety and tolerability of treatment will be summarized by the following:

- AEs
 - TEAEs
 - by PT
 - by PT nested within system organ class (SOC)
 - SAEs, by PT nested within SOC
 - AE leading to discontinuation, by PT nested within SOC
 - Potential hypersensitivity events

- AEs related to injection sites
- Suicide-related thoughts and behaviors
- Vital signs and weight
- ECGs
- Laboratory measurements
- Anti-drug antibodies (ADA) and neutralizing ADA (NAb)

Unless otherwise specified, safety analyses will be conducted for the GMB-treated population during GMB-treated time and GMB-treated time plus off-treatment time. Categorical safety analyses will include both scheduled and unscheduled visits.

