10.3.4. Safety Analyses

The safety and tolerability of treatment will be summarized by the following:

- AEs
 - TEAEs
 - By preferred term (PT)
 - By system organ class (SOC)
 - By maximum severity
 - By outcome
 - Considered to be related to treatment by investigator
 - SAEs
 - AEs leading to discontinuation
- Suicidal ideation and behaviors assessed by solicited questioning using the C-SSRS
- Vital signs and weight
- ECGs
- Laboratory measurements

Unless specified otherwise, the categorical safety analyses will include both scheduled and unscheduled visits.

Treatment-emergent adverse events are defined as the reported AEs that first occurred or worsened during the post-baseline phase compared with the baseline phase. For each TEAE, the severity level of the event (mild, moderate, or severe) will be determined by patient or physician

opinion. The Medical Dictionary for Regulatory Activities (MedDRA) Lowest Level Term (LLT) will be used in the treatment emergent computation. For each LLT, the maximum severity at baseline will be used as the baseline severity. If the maximum severity during postbaseline is greater than the maximum baseline severity, the event is considered to be treatment emergent for the specific post-baseline phase. For each patient and TEAE, the maximum severity for the MedDRA level being displayed (PT, High level Term, or SOC) is the maximum post-baseline severity observed from all associated LLTs mapping to that MedDRA level.

For events that are gender-specific, the denominator and computation of the percentage will include only patients from the given gender.

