- Safety analyses are reduced to summaries of AE overview, TEAE, SAE, and DCAE, since detailed planned analyses of Study CGAR safety data are more thoroughly described in PSAP for cluster headache indication in the context of combining the safety data from the originating studies with the safety data from Study CGAR.
- Section 5.17. Reports to Be Generated at Each Interim and Final Database Lock was added.
- Other minor corrections, modifications, and clarifications were made.

Statistical Analysis Plan Version 3 was approved prior to the final study database lock. The overall changes and rationale for the changes incorporated in Version 3 are as follows:

- General formatting and grammatical edits were made to improve clarity.
- The PGI-I analyses in Section 5.13 were updated to remove a graphical display; a tabular summary will be presented instead, without 95% confidence intervals.
- The description of the EQ-5D-5L questionnaire was updated in Section 5.14 to provide additional details for the derivation of the health state index scores. A description of the correlation analyses of EQ-5D-5L with PGI-I and cluster headache status was also added to meet the stated tertiary objectives.
- The following safety analysis descriptions were added in Section 5.16, to be consistent with the analysis approaches described in the SAPs for the other Emgality Phase 3 cluster headache studies:
 - Potential hypersensitivity events (Section 5.16.2)
 - AEs related to injection sites (Section 5.16.3)
 - Upper Respiratory Tract Infections (Section 5.16.4)
 - Suicide-related thoughts and behaviors (Section 5.16.5)
 - Vital signs and weight (Section 5.16.6)

- Electrocardiogram Intervals and Heart Rate (Section 5.16.7)
- Laboratory tests (Section 5.16.8)
- Immunogenicity (Section 5.16.9)
- The data cutoff dates for the two interim database locks were added in Section 5.17.1 for the interim locks used to support the regulatory submission and safety update report, respectively.
- The list of important protocol deviations in Appendix 1 were updated to align with the current version of the Trial Issue Management Plan (Version 12).

4. Study Objectives

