5.4. General Considerations

General aspects of statistical analyses are described below.

Unless otherwise specified, analyses will be conducted in the GMB-treated population, which includes all patients who are enrolled and receive at least 1 dose of study drug in Study CGAR, and analyses will be presented with 1 treatment arm. Safety analyses will be performed during the GMB-treated time and during the whole open-label treatment phase (SP II), which includes both GMB-treated time plus off-treatment time. GMB-treated time is composed of monthly dosing intervals, that is, the time from a GMB dose to the next monthly visit. The time between the first monthly visit that a dose is not administered and the dosing re-initiation visit is counted as off-treatment time. Baseline will be the time during SP I prior to receiving the first dose in this study. For safety analyses during the open-label treatment phase, any time after the first dose of GMB 300 mg will be considered as postbaseline period no matter if it is during an on-treatment or off-treatment month. For safety analyses during the GMB-treated time, only events that occurred during the GMB-treated time will be considered as postbaseline values.

Statistical analysis of this study will be the responsibility of Lilly or its designee. SAS[®] software will be used to perform most or all statistical analyses.

Any change to the data analysis methods described in the protocol will require an amendment ONLY if it changes a principal feature of the protocol. Any other change to the data analysis methods described in the protocol, and the justification for making the change, will be described in the SAP or clinical study report (CSR). Additional exploratory analyses of the data will be conducted as deemed appropriate.

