5.16.1. Treatment-Emergent Adverse Events

Treatment-emergent AEs are defined as the reported AEs that first occurred or worsened during the postbaseline phase compared with baseline phase. For events occurring on the day of first administration of study drug, the case report form collected flag will be used to determine whether the event was pre-treatment versus post-treatment. For each TEAE, the severity level of the event (mild, moderate, or severe) will be determined by patient or physician opinion. The Medical Dictionary for Regulatory Activities (MedDRA) Lowest Level Term (LLT) will be used in the treatment-emergent computation. For each LLT, the maximum severity at baseline will be used as the baseline severity. If the maximum severity during postbaseline is greater than the maximum baseline severity, the event is considered to be treatment emergent. For events with a missing severity during the baseline period, it will be treated as “mild” in severity; for events with a missing severity during the postbaseline period, it will be treated as “severe” for TEAE computation. For each patient and TEAE, the maximum severity for the MedDRA level being displayed (PT, High Level Term, or SOC) is the maximum postbaseline severity observed from all associated LLTs mapping to that MedDRA level.

For events that are male- or female-specific, the denominator and computation of the percentage will only include patients from that specific sex.

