5.16.4. Upper Respiratory Tract Infections

Upper respiratory tract infections will be defined using all the PTs from the 2 High Level Terms of “upper respiratory tract infections” and “upper respiratory tract infections NEC” as defined in MedDRA.

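### Does the SAP lose TEAE summaries by severity, outcome and relatedness that the protocol planned for CGAR alone?

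*SAP*

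**What the plan says.** Protocol 10.3.4 sets out how TEAEs are to be summarised. Besides preferred term and system organ class, it lists "By maximum severity", outcome, and "Considered to be related to treatment by investigator". Protocol 10.3.3 asks for the Month 1 PGI-I response (score 1 or 2) as a proportion with an exact 95% confidence interval.

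SAP 5.16 introduces its own list with "For the purpose of Study CGAR alone, the safety and tolerability of treatment will be summarized by the following". Under TEAEs it names two tables: by preferred term, and by preferred term within organ class. Serious events and events leading to discontinuation follow, each by preferred term within organ class. SAP 5.16.1 retains a severity rule: for each patient and event, "the maximum severity for the MedDRA level being displayed (PT, High Level Term, or SOC) is the maximum postbaseline severity observed". It names no table that uses the rule. No SAP section names a TEAE table by outcome or by relatedness. SAP 5.13 keeps the PGI-I proportion and does not mention an interval.

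The SAP comments on both reductions. The Version 2 entry in Section 3 says the safety analyses were cut back "since detailed planned analyses of Study CGAR safety data are more thoroughly described in PSAP for cluster headache indication". Section 5.16 adds: "The planned integrated analyses are described in separate documents". The Version 3 entry says the PGI-I analyses in 5.13 now use a table without 95% intervals in place of a graph. SAP 5.4, like Protocol 10.3.1, gives the rule for changes that need no amendment: "Any other change to the data analysis methods described in the protocol, and the justification for making the change, will be described in the SAP", and the sentence goes on to offer the clinical study report as the alternative place.

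**The concern.** TEAEs are the first-listed primary endpoint of a single-arm safety study. With no comparator, readers rely on severity and causality judgements to interpret event counts. A table by preferred term shows how many patients had an event, but not how bad it was or whether the investigator thought the drug caused it. Tables of serious events and discontinuations leave out the remaining TEAEs. SAP 5.17.2 ties the final-lock output to the analyses defined in the SAP, so a table the SAP does not name is not promised.

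If the protocol's breakdowns had been dropped without a word, the CGAR-alone report would be thinner than planned and a reader would not know why. The missing PGI-I interval looks like the same thing on a smaller scale: an estimate stripped of the precision the protocol attached to it.

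**Working it through.** The TEAE part is a comparison of text. The documents give no sample size, event count or response rate to reproduce.

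**Step 1. TEAE breakdowns.**

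| Protocol 10.3.4 | In the SAP |
|---|---|
| Preferred term | Named, 5.16 |
| System organ class | Named, 5.16 (as preferred term within class) |
| Maximum severity | Derivation in 5.16.1, no table named |
| Outcome | Absent |
| Investigator-judged relatedness | Absent |

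Named 2 + derivation only 1 + absent 2 = 5.

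**Step 2. Is the list in 5.16 a complete inventory?** It is not. Upper respiratory tract infections are missing from it, yet SAP 5.16.4 defines them ("Upper respiratory tract infections will be defined using all the PTs from the 2 High Level Terms"). The AE overview is missing too, although the Version 2 history names it among the retained safety summaries and 5.17.1 names it for the interim locks. Its content is not defined, so the documents neither show nor rule out severity or relatedness counts within it.

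**Step 3. Does the severity rule have a use?** Treatment emergence is decided at the Lowest Level Term. The sentence in 5.16.1 assigns a maximum severity at the level being displayed, which the emergence calculation does not need. It serves a display by severity. The gap there is an unnamed table, and the method is already set.

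**Step 4. Is the information kept?** Protocol 9.2 has investigators judge relatedness yes or no and record it in the eCRF. SAP 5.16.1 assigns every TEAE a severity and says how missing severities are treated. Both tables can be produced from the database at any time. The documents do not show whether AE outcome is a collected field, so that table cannot be judged either way.

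**Step 5. Is the primary endpoint still analysed?** Protocol Table 4.1 and SAP 4.1 define it through TEAEs, serious events and the C-SSRS, with no breakdown specified. SAP 5.16 and its subsections cover all three and add discontinuations due to adverse events, likely hypersensitivity events and injection-site events.

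**Step 6. The PGI-I interval.** With x responders among n patients, the exact (Clopper-Pearson) limits are the 0.025 quantile of Beta(x, n − x + 1) and the 0.975 quantile of Beta(x + 1, n − x). Since n and the response rate are not given, these are assumed values:

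| n | 40% response | 50% response | 80% response |
|---|---|---|---|
| 50 | 26.4–54.8% (width 28.4) | 35.5–64.5% (28.9) | 66.3–90.0% (23.7) |
| 100 | 30.3–50.3% (19.9) | 39.8–60.2% (20.3) | 70.8–87.3% (16.5) |
| 200 | 33.2–47.1% (14.0) | 42.9–57.1% (14.3) | 73.8–85.3% (11.5) |

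Widths are in percentage points, taken before the limits are rounded, and are largest at 50% response. The interval needs only x and n. SAP 5.13 also summarises PGI-I as a categorical variable at each time point, so a standard table would show both.

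**The case for a change.** The best case for a change has three parts.

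First, the Version 2 reason points to an integrated plan. SAP 5.16 itself separates the integrated analyses, which add parent-study data, from CGAR alone. Pooled tables would not by themselves supply CGAR-alone ones.

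Second, Version 3 restored eight safety topics to match the other Phase 3 cluster headache studies and did not restore these breakdowns.

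Third, the stated reason names none of the missing items, and the PGI-I entry gives no reason at all. Its wording is also tied to replacing a graph, so it may not have been meant for the Month 1 proportion.

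These observations are accurate. What stands is a minor inconsistency between the two documents and an incomplete explanation. The change rule does not require each dropped table to be listed, and it accepts a justification in the clinical study report, which was not available here. The reduction was disclosed with a general reason before the interim lock for submission. As for the interval, the Month 1 proportion sits in Section 5.13, the section the Version 3 entry says was updated, so the natural reading includes it.

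The value of the missing tables should not be overstated either. Every analysed patient receives open-label galcanezumab, so the investigator judges causality knowing the treatment, and there is no untreated group to set against it. A relatedness table helps description but does not settle attribution.

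**Conclusion.** The difference in text is confirmed, and no change to the plan follows. Two of the five TEAE breakdowns are named, one is derived without a named table, and two are absent. Of those two, outcome depends on a field the documents do not show to be collected, so relatedness is the only firm omission. Followed as written, the SAP gives sound TEAE, serious-event, discontinuation and C-SSRS results. No estimate is biased, no test is affected, and no conclusion would differ with the extra descriptive tables.

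The PGI-I interval is smaller still. The endpoint is tertiary and descriptive. The uncertainty left unstated is 11.5 to 28.9 points of width over the assumed 40–80% response and n of 50 to 200, and a reader can recover it from the count and denominator.

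This conclusion assumes that severity and relatedness are recorded as the documents describe, and that the PGI-I table shows its denominator, as a categorical summary normally does. It does not rely on the integrated analyses or the study report containing the missing tables, since neither could be checked.
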